7.7 Boost Technique with Image Guidance (IGRT)

IGRT Target Localization: Cone-beam CT (CBCT) images will be acquired weekly prior to treatment. By using weekly IGRT to image the post-operative tumor bed of the breast in “real-time”, the operator will be able to align the tumor bed with the treatment machine for each subsequent tumor bed treatment. If the resection cavity is not visualized then cone-beam CT images will be used to ensure optimal positioning of the breast tissue. A portal image of each boost treatment field will be acquired following CBCT.

8 TOXICITIES TO BE MONITORED AND DOSAGE MODIFICATIONS

1. Expected acute toxicities include fatigue and skin reactions within the radiation field. Erythema, dry and wet desquamation of the skin will be recorded weekly, during RT treatment. The toxicities will be graded by the research nurses assigned to the study according to Common Terminology Criteria for Adverse Events, version 5.0, and Late Effects on Normal Tissues/ Subjective, Objective, Management and Analytic criteria (LENT/SOMA) for acute and late toxicity, respectively.
2. The risks involved in using the treatment machine or the CT scanning are described in the regular informed consent given to all patients undergoing radiation therapy.

8.1 Cosmetic results assessment

Breast cosmesis will be assessed using the Breast Cancer Treatment Outcome Scale (BCTOS) patient self-reports before treatment (baseline), at the end of RT, at 1-month follow up visit and at 2-year follow up visit. This brief self-report instrument has high reliability and validity and has been used in a variety of previous studies on recovery from breast cancer treatment. [25]. The BCTOS also will be used as a primary measure to assess breast-related symptoms and treatment effects. The receipt of the survey will be recorded by the research nurses assigned to the study, but completion is not mandatory. Quality of life surveys will be sent to the patients’ personal email address at the baseline, at the end of RT, at 1-month follow up visit and at 2-year follow up visit. Completed responses will be sent directly to our REDCAP database. The quality of life survey completion is optional.

8.1.1 Measuring the late toxicities of breast radiation

Radiation-induced breast fibrosis is another important late effect of radiotherapy with a commonly reported incidence of 5-15%. Clinically, radiation-induced breast fibrosis is characterized by skin retraction, atrophy, toughness to palpation, and decreased tissue compliance with associated functional limitations. Visual assessment and palpation are the most important clinical investigations of the skin in radiotherapy but they are subjective and unquantitative. The LENT/SOMA scoring system will be used in the reporting of late radiation morbidity in this protocol [24]. We will obtain measurement of breast fibrosis at baseline (prior to treatment) and at each subsequent follow-up after completing radiotherapy, scored by the research nurses assigned to the study.

9 STUDY CALENDAR

All patients will be followed a month after the completion of treatment. Our routine follow up is once a year after completion of radiation therapy. **For the purpose of protocol significance (for assessment of fibrosis), we will require at least one follow up in the department visit after the**

second year. Acute and late effects will be recorded following the criteria described in Appendix 1. At each post treatment follow-up visit, a physical exam to detect clinical recurrence will be performed. Mammographic studies and/or MRI will be performed and reviewed on an annual basis.

The degree of fibrosis assessed by palpation will be measured as per Appendix 1, late effects at 2-3 years and at 5 years. Local control at 2-3 years and at 5 years will be extracted from the medical record, and can be derived from clinical reports from medical, surgical or radiation oncologists as well as from the primary care doctor who is following the patient.

Table 4: Study Calendar

Study	Pre Entry	Weekly[‡]	Post Treatment Follow-up visits
Mammogram	X		X**
Lumpectomy pathology report	X		
Medical History	X		X*
BCTOS and quality of life surveys[⊕]	X		X
Physical exam	X	X	X*
Consent Form	X		
Randomization	X		
Treatment simulation	X		
Weekly CBCT prior to RT treatment		X	
Port films/ each RT dose after the first one		X	
Skin Assessment	X	X	X*

[‡] - performed weekly during the weeks of radiation therapy.

* Our routine follow up is once a year after completion of radiation therapy. For the purpose of protocol significance (for assessment of fibrosis), we will require at least one follow up visit after the second year.

** Standard annual mammogram (or MRI) for both breasts will be accepted as follow up data.

⊕ Quality of life surveys will be sent to the patients' personal email address. Completed responses will be sent directly to our REDCAP database. The quality of life survey completion is optional. The receipt of the BCTOS survey will be recorded by the research nurses assigned to the study, but completion is not mandatory. The BCTOS and quality of life questionnaires will administer before treatment (baseline), at the end of RT, at 1-month follow up visit and at 2-year follow up visit.

10 CRITERIA FOR EVALUATION AND ENDPOINT DEFINITIONS

- Acute and late toxicity will be reported as scheduled in the above study calendar (10.1) following the criteria in Appendix 1.
- Local recurrence will be classified as it follows:
- Local recurrence within the field of conformal radiation is defined as TRUE LOCAL RECURRENCE.
- Axillary/ intra-mammary or supraclavicular recurrence in the same side of the index lesion will be defined as REGIONAL RECURRENCE /SAME BREAST.
- At the time of local recurrence all patients will undergo disease assessment with CT of Chest/ Abdomen/ Pelvis and, if symptomatic, bone scan and/or brain MRI.
- Local/regional recurrences will be further grouped as:
- ISOLATED LOCAL/REGIONAL RECURRENCES
- CONCOMITANT LOCAL/REGIONAL AND DISTANT RECURRENCES

Patients developing local recurrences after systemic recurrence has been documented will be classified as:

- METACRONOUS LOCAL/REGIONAL RECURRENCES.
- CONTRALATERAL BREAST CANCER will also be recorded and reported as invasive and noninvasive.

11 STATISTICAL AND DATA MANAGEMENT CONSIDERATIONS

Study Design: This study is a prospective randomized controlled trial to test the hypothesis that whole breast radiotherapy to 3200cGy with a concomitant tumor bed boost to 4200 cGy in 10 fractions (Arm 2,) is not inferior to standard whole breast radiotherapy with a concomitant tumor bed boost to 4800 cGy to the tumor bed in 15 fractions (Arm 1).

A total of 400 patients will be randomized to arm 1 or 2 to test the primary hypothesis that the proportion of patients with grade ≥ 2 acute toxicity with 2 weeks regimen would not be $> 5\%$ greater than the rate of 10% with a standard 3weeks regimen, with a 1-sided α of 0.025 and power of 79%.

The trial will have 2 planned interim analyses at 80 patients (20%; rejecting the null hypothesis when $Z \leq -4.88$, or $P \leq 0$) and at 240 patients (60%; rejecting the null hypothesis when $Z \leq -2.67$, or $P \leq 0.0038$) and a final analysis at 400 patients (100%; rejecting the null hypothesis if $Z \leq -1.98$, or $P \leq 0.0238$). The secondary objective was to test whether a significant difference exists between the 2 arms for long term fibrosis or telangiectasia grade ≥ 2 . The secondary objective has 1 planned interim analysis when 50% of the patients had completed 3 years of post-treatment follow-up (rejecting the null hypothesis if the hazard ratio was ≤ 0.37 , or $P < 0.0031$) and a final analysis when all the patients

had completed 3 years of follow-up (rejecting the null hypothesis if the hazard ratio was ≤ 0.63 , or $P < 0.049$).

The distributions of the baseline patient and disease characteristics at randomization for each arm will be summarized using descriptive statistics. Quantitative variables were summarized using the means, standard deviations, medians, and ranges; qualitative variables were summarized with frequency distributions of the nominal levels. Wilcoxon rank sum tests were used to compare the distributions of the quantitative variables between the 2 arms, and Fisher exact tests were used to compare the distributions of the qualitative variables between the 2 arms.

To summarize the safety data, distributions of toxicity grades will be provided by treatment arm. Noninferiority tests will be conducted to test the primary hypothesis that the 2 weeks regimen would result in no more toxicity than did the 3 weeks regimen. Fisher exact tests will be used to compare the distributions of acute and late toxicity grades between the 2 weeks arm and the 3 weeks arm.

The comparison of the cumulative incidence of long term fibrosis or telangiectasia grade ≥ 2 between the 2 arms will be conducted using log-rank χ^2 tests. The hazard ratio between the 2 arms will be computed with the 95% confidence intervals.

Local recurrence-free survival will be estimated for both treatment arms using Kaplan-Meier curves, the relative risk will be estimated, and the 2 arms will be compared using the log-rank χ^2 tests.

11.1 Data management:

Data Management will be carried out by staff of the Department of Radiation Oncology at WCMC under the direction of [name]. Randomization will occur from a randomization list provided by [name]'s team and allocation to each arm will be performed, after consent is acquired, by the research team in the department of Radiation Oncology. The Randomization will be a manual process where the data manager will enter the consented patient's name in a sequential order in the Randomization list provided. Data will be entered into the JCTO Clinical database management system maintained by the JCTO according to the procedures of WCM. Patients will be followed every 12 months to evaluate their status with respect to recurrence. Recurrences will be evaluated using standard criteria in the Dept. of Radiation Oncology that are provided in the protocol. Data will be transferred from the Clinical database to the Division of Biostatistics for analysis. The Principal Investigator, Research Nurse and Data Manager have access to data collected.

Analysis: Patient characteristics at randomization will be summarized by treatment group using descriptive statistics and graphical displays.

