Summary of changes for Protocol version 2.2 dated 13OCT2020.

Section(s)	Changes	Rationale
Study Team	Adding [name] to the study team as key personnel. Removing [name] and [name] from the Personnel section	Personnel changes

Summary of changes: Version 2.1 Dated 23MAR2020

Sections 6.1.6, section 8.1 and section 9 have been modified to include the following statement:

“Quality of life surveys will be sent to the patients’ personal email address. Completed responses will be sent directly to our REDCAP database.”

Summary of Changes: Version 2.0 Dated 18NOV2019

1. Page 8 Hypothesis: ARM 2 boost dose was incorrect and has been changed to 4200cGY.
2. Page 6 schema had N0-1 and this has been changed to N0. This has been made consistent across the protocol.
3. Section 7.3 Treatment duration section has been revised to state that, the whole breast will be treated for five consecutive fractions for either three (Arm 1) or two (Arm 2) consecutive weeks.

[figure not shown]
Informed Consent changes:

1. The footer of the informed consent has been changed to indicate the correct version of the protocol.

No other changes have been made in the informed consent.

SCHEMA

These exams, tests or procedures are part of regular cancer care and may be done even if you do not join the study.

Protocol Summary

Full Title: Prospective Randomized study of Accelerated Radiation Therapy (PRART): a Non-Inferiority Trial to Compare Breast Cosmesis and Local Control after Concomitant Boost Breast Radiotherapy with Fifteen Fractions in Three Weeks (arm 1, standard) versus Ten Fractions in Two Weeks (arm 2, experimental)

Short Title: Randomized

Clinical Phase: Phase III

Principal Investigators: Drs. [name] and [name]

Sample Size: N= 400 (200 per Arm)

Accrual Ceiling: 430

Rate of subject accrual: Approx. 8 subjects per month or 100 patients per year

Study Population: S/p segmental mastectomy patients with Tis (DCIS), T1-T2, N0 breast cancers.

Accrual Period: 4 years

Study Design: Patients with Tis (DCIS), T1-T2, N0 breast cancers will be randomized to receive whole breast radiotherapy with a concomitant boost to the tumor bed over 15 fractions (Arm 1, standard) versus 10 fractions (Arm 2, experimental).

Study Duration: 10 years to report: 2-3 years and 5 years late toxicity, local control rate, and breast cosmesis.

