Intervention Description: Radiotherapy: 4050cGy whole breast radiotherapy with a concomitant tumor bed boost to 4800 cGy to the tumor bed in 15 fractions (Arm 1) versus 3200cGy whole breast radiotherapy with a concomitant tumor bed boost to 4200 cGy in 10 fraction (Arm 2).

Hypothesis: A regimen of whole breast radiotherapy to 3200cGy with a concomitant tumor bed boost to 4200 cGy in 10 fractions (Arm 2) is not inferior to the current standard of whole breast radiotherapy of 4050 cGy with a concomitant tumor bed boost to 4800 cGy in 15 fractions (Arm 1), in terms of acute toxicity and long-term fibrosis, breast cosmesis and local control, at 2-3 years and at 5 years.

Primary Objectives: 1. To prospectively randomize patients to one of two hypo-fractionation regimens of concomitant boost breast radiotherapy as part of breast conservation therapy in patients with T1-2N0 breast cancers or Stage 0 (Tis) DCIS: 4050cGy whole breast radiotherapy with a concomitant tumor bed boost to 4800 cGy to the tumor bed in 15 fractions (Arm 1) versus 3200 cGy whole breast radiotherapy with a concomitant tumor bed boost to 4200 cGy in 10 fractions (Arm 2).

2. To test the primary hypothesis that the proportion of patients with grade ≥ 2 acute toxicity with 2 weeks regimen (10 fraction arm) would not be $> 5\%$ greater than the rate of 10% with a standard 3weeks regimen (15 fraction arm).

Endpoints:

Primary endpoint is the rate of acute toxicity. Expected acute toxicities include fatigue and skin reactions within the radiation field. Erythema, dry and wet desquamation of the skin will be recorded weekly, during RT treatment. The toxicities will be graded by the research nurses assigned to the study according to Common Terminology Criteria for Adverse Events, version 5.0.

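### The stated 79% power does not follow from the plan's inputs: if both arms truly have a 10% rate, 200 per arm gives about 38%

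*Combined protocol and SAP*

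**What the plan says.** Section 11 gives the design of the primary test: "A total of 400 patients will be randomized to arm 1 or 2", with the aim of showing that the grade ≥2 acute toxicity proportion on the 2-week regimen is not more than 5% "greater than the rate of 10% with a standard 3weeks regimen". It gives the operating characteristics as "with a 1-sided α of 0.025 and power of 79" per cent. The Protocol Summary gives the allocation as "N= 400 (200 per Arm") and repeats the 10% rate and the margin under Primary Objectives.

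There are interim looks at 80 and 240 patients and a final analysis at 400, with Z boundaries of −4.88, −2.67 and −1.98.

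No true Arm 2 rate is given for the power calculation, and no formula. Later in Section 11 the primary hypothesis is worded as "the 2 weeks regimen would result in no more toxicity than did the 3 weeks regimen".

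**The concern.** A power figure for a non-inferiority test means little without the assumed true rate in the experimental arm. The usual convention is equal true rates, and the plan's own wording of non-inferiority suggests nothing else. On that basis 200 per arm is far too few for a 5-point margin around a 10% rate.

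The primary conclusion rests on this design. If the arms are in fact the same, a miss is the more likely result, and a reader who believes the trial had 79% power could take that miss as evidence that the 2-week regimen is more toxic. The IRB and the DSMB also have the 79% figure in front of them.

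**Working it through.** **Inputs.** From Section 11: control rate 0.10, margin 0.05, one-sided α 0.025, stated power 79%, final boundary Z ≤ −1.98. From the Protocol Summary: n = 200 per arm. The true Arm 2 rate is not stated; equality at 0.10 is assumed first, and other values are tabulated below.

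**Attempt to reproduce 79%** (unpooled normal approximation):

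- SE = √(2 × 0.10 × 0.90 / 200) = 0.030
- margin / SE = 0.05 / 0.030 = 1.667
- power = Φ(1.667 − 1.960) = 38.5%
- with the final critical value: Φ(1.667 − 1.98) = 37.7%

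**Allowing for the interim looks.** The three boundaries together give an overall one-sided α of 0.0250, so the error spending is consistent with the stated α. Power under the full boundaries is 38.2% by the multivariate normal calculation. Simulating 400,000 trials with looks at 40, 120 and 200 per arm gives 39.1% with the unpooled statistic and 37.2% with the Farrington–Manning statistic.

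**Other test formulas.** Using the null variance at 10% and 15% gives 31.3%; the arcsine method gives 33.0%. The choice of formula does not explain the gap.

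**What would give 79%, changing one input at a time:**

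- Sample size: (1.96 + 0.806)² × 2 × 0.09 / 0.05² ≈ 551 per arm (552 when rounded up).
- Margin: (1.96 + 0.806) × 0.030 = 8.3 points.
- Common true rate: 3.4%. SE = √(2 × 0.0338 × 0.9662 / 200) = 0.0181, and 0.05 / 0.0181 ≈ 2.77.
- True Arm 2 rate with Arm 1 at 10%: 7.24%. SE = √((0.09 + 0.0724 × 0.9276) / 200) = 0.0280, and (0.15 − 0.0724) / 0.0280 ≈ 2.77.
- One-sided α of 0.20 gives 79.5%, but this contradicts both the stated α and the stated boundaries.

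**Alternative readings.** A one-sample test against a fixed 15% gives 47% (exact) to 65% (normal approximation) at n = 200, and 82% (exact) to 92% at n = 400. Reading the 5% margin as relative (0.5 points) gives about 4%. Neither yields 79%.

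**Power by true Arm 2 rate** (Arm 1 at 10%, 200 per arm, fixed design):

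| Arm 2 rate | Power |
|---|---|
| 5% | 96.8% |
| 6% | 91.4% |
| 7% | 81.9% |
| 8% | 68.7% |
| 9% | 53.5% |
| 10% | 38.5% |
| 11% | 25.6% |

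**What a success requires.** Suppose Arm 1 has 20/200 events.

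- Arm 2 at 18/200: Z = (0.09 − 0.10 − 0.05) / √((0.09 × 0.91 + 0.10 × 0.90) / 200) = −0.060 / 0.0293 = −2.05, which passes −1.98.
- Arm 2 at 19/200: Z = −0.055 / 0.0297 = −1.85, which fails.

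Arm 2 must therefore look better than the control, not merely similar. Equivalently, the 95% confidence interval half-width is 1.96 × 0.030 = 5.9 points, wider than the 5-point margin.

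**Accrual ceiling.** If all 430 were analysed (215 per arm), SE = √(0.18 / 215) = 0.0289 and power is 40.8%. The ceiling was raised to replace withdrawals and secure 400, so it does not close the gap.

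**The case against.** The strongest reply is that equality of the true rates is not written in the plan. Power depends heavily on the Arm 2 rate, as the table shows, and a rate near 7.2% reproduces 79% almost exactly. The background also leans towards lower toxicity. Section 2.2 reports less acute toxicity with a shorter regimen. Table 1 in Section 2.3 gives lower whole-breast equivalent doses for Arm 2 at every α/β; at 10 Gy they are 35.2 against 42.8, and the boost is 49.7 against 52.8. On this view, the sponsor may have assumed a favourable alternative and left it out of the text.

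Part of this stands. The 38% is conditional on equal 10% rates, and the sponsor may have had another alternative in mind. But the background does not supply one. The Section 2.2 statement is about the group's earlier trials of longer schedules, with no rate for ten fractions. Section 2.3 links the lower breast dose to fibrosis and cosmesis, which are late effects. Nothing ties either passage to the sample size. If a 7.2% rate was intended, the whole design rests on an unstated and unjustified assumption, which also has to be corrected.

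It is also fair to say that the plan does not state how a miss would be interpreted. The risk of misreading is a judgement about readers, not a contradiction in the text.

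**Conclusion.** The concern holds. With 200 per arm, a 10% control rate, a 5-point margin and one-sided α of 0.025, power at equal true rates is about 38–39% against the stated 79%, a shortfall of about 40 points. Under that condition the trial fails to show non-inferiority about 61–62% of the time (100 − 39 to 100 − 38). The result rests on equal true rates of 10% and on reading the margin as absolute, which is the reading more favourable to the plan. It does not depend on the test formula or on the interim looks. The plan states no alternative that gives 79%. Because this is the power of the only primary hypothesis, it must be corrected.

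**What to change.** Amend Section 11 in one of two ways, and carry the assumed rates into the Protocol Summary:

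1. Replace the 79% with about 38–39% at equal true rates of 10% for 400 analysed patients (about 41% if 430 were analysed); or
2. Keep 79%, state the assumption under which it holds (a true Arm 2 rate of about 7.2% against 10%), justify it, and give the power at equal rates beside it.

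In either case, name the test statistic and formula used. Add the expected 95% confidence interval half-width of ±5.9 points, and state that failure to reject will be reported as inconclusive, with the interval, and not as evidence of inferiority. This should be in place before the final analysis, because the same wording added after a miss would carry little weight.

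The cost is a text amendment and a less favourable power figure. No extra patients are needed, and the treatment and interim boundaries stay as they are.

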13.2.2 Serious adverse events

Adverse events classified as serious require expeditious handling and reporting to comply with regulatory requirements. All serious adverse events, whether considered to be drug-related or not, require that a Serious Adverse Event Report Form be completed within 24 hours of the investigator becoming aware of the event. The investigator must immediately report all unexpected serious adverse events to the Institutional Review Board in writing.

Serious adverse events will be reported to:

[name]. [name] [contact] [contact]
--

14 Sub Sites:

Sub-sites participating in the trial will be given access to REDCAP e-CRFs to document adverse events based on CTCAE v5.0 in REDCAP routinely. We request that the sites complete the REDCAP baseline e-CRFs within 7 days from enrolling the patients. Adverse events have to be documented in REDCAP routinely during every follow-up visit.

Serious adverse events will be documented as per sub-site's institutional guidelines. We request sub-sites to notify [name] within 24 hours of the sub-site becoming aware of the event. Serious Adverse Events will be reported to WCMC's data safety monitoring board every 6 months.

15 Medical Monitor

This study will be monitored by the WCM Data Safety Monitoring Committee according to the procedures of the WCM Data Safety Monitoring Plan. The DSMB will be monitoring Grade 3 and above adverse events throughout the course of the study. In addition, the DSMB will also be reviewing SAE reports submitted by the study team, based on the DSMB guidelines. The WCM DSMB committee will be the medical monitor of the study.

15.1 Sub-sites:

Sub-sites will monitor the study locally and must follow sub-site's institutional guidelines. Waivers, exceptions and serious adverse events must be reported to the WCM team as and when the event occurs.

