15.3 Stopping Rules

For patients experiencing Grade 3 and above adverse events, treatment will be suspended until the resolution of the adverse events to baseline.

15.4 Sub-sites:

Sub-sites should use the local Data safety Monitoring board to monitor the studies. Data safety reports and approvals must be sent to the WCM team for regulatory purposes.

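### The interim plan states no between-arm harm guideline on grade ≥2 acute toxicity, the quantity the trial tests

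*Combined protocol and SAP*

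**What the plan says.** - **Primary hypothesis (Protocol Summary; Section 11).** The rate of grade ≥2 acute toxicity in Arm 2 should not exceed the 10% expected in Arm 1 by more than 5 percentage points, tested "with a 1-sided α of 0.025 and power of 79"%. The size is 400 patients, 200 per arm.
- **Interim looks (Section 11).** "The trial will have 2 planned interim analyses at 80 patients (20%; rejecting the null hypothesis when" Z ≤ −4.88, then at 240 patients when Z ≤ −2.67, with a final limit of −1.98 at 400. Each analysis has this one limit, on the side favouring Arm 2. No upper, harm or futility limit is given.
- **DSMB scope (Section 15).** "The DSMB will be monitoring Grade 3 and above adverse events throughout the course of the study". It also reviews serious adverse event reports. Section 15.2 sets safety reports every six months and gives no numerical threshold.
- **Stopping rules (Section 15.3).** "For patients experiencing Grade 3 and above adverse events, treatment will be suspended" until recovery. This concerns the individual patient and makes no comparison between arms.
- **Toxicity summaries (Section 11).** Grade distributions by arm are planned, but they are not tied to an interim look or to the DSMB.

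**The concern.** The experimental arm gives larger fractions over a shorter time, and acute toxicity is the primary endpoint. A monitoring plan for such a trial would normally say what happens if early data point the wrong way on that endpoint. Here the formal looks can act on a favourable result only, and the safety route is directed to more severe events than those being tested.

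Grade 2 events make up the part of the endpoint that lies outside the DSMB's stated scope. An excess confined to grade 2 could build up without any document requiring that the DSMB see it by arm, or saying what size of difference should prompt discussion. At stake is the exposure of patients still to be randomised: up to 160 after the second look, on the planned 400.

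**Working it through.** **Inputs.** Control rate 10%, margin 5 points, one-sided alpha 0.025, looks at 80, 240 and 400 (Section 11); 200 per arm (Protocol Summary). Assumed: an even split at each look (40 v 40, then 120 v 120) and, because Section 11 names no test statistic, an unpooled Z for the non-inferiority test.

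**1. The plan's own limits.** Lan-DeMets spending of the O'Brien-Fleming type, at information 0.2, 0.6 and 1.0, gives limits of 4.877, 2.669 and 1.981, with one-sided P of 5.4e-7, 0.0038 and 0.0238. The printed limits (4.88, 2.67, 1.98) agree, and their overall one-sided alpha is 0.0250. The efficacy side is sound.

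**2. What the plan does with an adverse result.** Take 30/120 in Arm 2 against 12/120 in Arm 1 at the second look.

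- Against the margin: Z = (0.25 − 0.10 − 0.05) / √(0.25×0.75/120 + 0.10×0.90/120) = 0.10/0.0481 = +2.08.
- Against no difference, with pooled rate 42/240 = 0.175: Z = 0.15 / √(2×0.175×0.825/120) = 0.15/0.0491 = +3.06.

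The only rule at this look is Z ≤ −2.67. A positive Z of any size meets no criterion, and 400 − 240 = 160 patients are still to be randomised.

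**3. Is the gap filled elsewhere?**

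| Place | Toxicity covered | Compares arms? | Threshold for the trial? |
|---|---|---|---|
| Section 11, looks at 80 and 240 | grade ≥2 | yes | favourable side only |
| Section 15, DSMB scope | grade ≥3 and SAEs | not stated | none |
| Section 15.2, six-monthly reports | safety reports | not stated | none |
| Section 15.3, stopping rules | grade ≥3 | no | single patient only |

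No row combines grade ≥2, a comparison of arms and an adverse-side threshold.

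**4. What a simple guideline would detect.** With n patients per arm, flag when Z = (p₂ − p₁) / √(2p̄(1 − p̄)/n) ≥ 2.33 (one-sided P<0.01), where p₁ and p₂ are the observed rates in Arms 1 and 2 and p̄ is their pooled value. The chance of a flag is the sum, over all pairs of counts that meet this, of the product of the two binomial probabilities, with Arm 1 at a true 10%:

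| True Arm 2 rate | Flag at 80 patients | Flag at 240 patients |
|---|---|---|
| 10% (equal) | 0.7% | 1.0% |
| 15% (the margin) | 4% | 12% |
| 20% | 13% | 44% |
| 25% | 29% | 78% |

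At equal rates the chance of a flag at either look is at most 0.7% + 1.0% = 1.7%.

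**The case against.** **There is safety oversight.** A DSMB acts as medical monitor, receives reports every six months, and works under an institutional Data Safety Monitoring Plan that is not in the file. It may already see grade 2 rates by arm and may act on judgement. The change log attributes the grade 3 scope to a DSMB memo of May 2022, so the choice was considered. Watching severe events while testing milder ones is defensible, and Section 1 itself lists acute toxicity of grade 3 or higher as an objective. This stands as far as it goes: a reader might infer that toxicity goes unmonitored, and the documents do not support that. They still give no guideline on the grade ≥2 rate that the trial was sized to test.

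**The looks may be past.** Version 7.0 (December 2024) raised the accrual ceiling from 420 to 430, because of withdrawals, to secure 400 patients. The documents give no accrual count, but this suggests that both looks may have gone by. It limits the benefit and is why the remedy must also work at a routine review.

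**The guideline is weak for small excesses.** This is true: it fires in only 12% of trials at 240 patients when Arm 2 is truly at the margin. It is a guard against a large excess, and the cut-off of 0.01 is a choice.

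**Two stronger readings are tempting.**

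- Section 11 prints the first limit's P-value as P ≤ 0, which might suggest an impossible or invalid look. It is a rounding of about 5e-7 beside a correct Z limit. Crossing needs about 0/40 against 13/40 (16 or 17 in Arm 1 with pooled or score tests), which is the ordinary conservatism of this boundary at 20% information.
- A reader might infer that crossing at 240 ends accrual and shrinks the sample for fibrosis and local control. Section 11 speaks only of rejecting the null hypothesis, and states that 400 patients will be randomised.

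**Conclusion.** The point holds in a limited form. Both primary-endpoint looks carry only a rule for declaring non-inferiority, and no document in the file states a between-arm harm guideline on grade ≥2 acute toxicity. This follows from the text and does not depend on the choice of test statistic. The efficacy limits are valid and no error in them is claimed.

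The gain from closing the gap depends on the true excess: substantial by 240 patients at 25% v 10% (78%), moderate at 20% v 10% (44%), and small at 15% v 10% (12%). These figures assume a true 10% in Arm 1 and an even split. The practical value also depends on how many patients remain to be randomised or treated, which the documents do not say.

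**What to change.** In Section 11, state that the DSMB receives grade ≥2 acute toxicity rates by arm at each primary-endpoint look, with a pre-specified, non-binding harm guideline, for example one-sided P<0.01 that Arm 2 is worse. Add a cross-reference in Section 15, so that the DSMB's stated scope includes this table. If the looks at 80 and 240 have passed, supply the table at the next six-monthly review and record which arm-level data the DSMB saw at each look.

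The cost is a wording amendment and one table per look. The weekly toxicity grading already yields the data. The guideline uses no alpha, because halting for harm can only lower the chance of a false non-inferiority claim. The downside is a false flag in about 1% of trials per look at equal rates, which the DSMB can overrule.
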